6. MILESTONES

The main milestones for the Drug Utilisation Study (DUS) will be:

Table 4 - Main study milestones

Start of data collection	Q3 2016
Interim report (planned)	Q3 2017
Planned end of data collection	Q4 2018
Final study report	Q2 2019 (latest 6 months after data base lock)

Recruitment will be performed in waves, as described in Table 5 (current planning dates – may be subject to change).

Table 5 - Milestones per country

Country	First Patient In (FPI)	Last Patient In (LPI)	Wave
Switzerland	Q3 2016	Q3 2017	I
Germany	Q3 2016	Q3 2017	I
United Kingdom	Q3 2016	Q3 2017	I
Belgium	Q3 2017	Q3 2018	II
Italy	Q3 2017	Q3 2018	II
Spain	Q3 2017	Q3 2018	II
Portugal	Q1 2018	Q4 2018	II

7. RATIONALE AND BACKGROUND

Edoxaban has been approved by the U.S. Food and Drug Administration FDA, the Swissmedic and by the European Medical Agency (EMA). In the EU it is approved for the following indications:

- Prevention of stroke and systemic embolism in adult patients with NVAF with one or more risk factors, such as congestive heart failure, hypertension, age ≥ 75 years, diabetes mellitus, prior stroke or transient ischemic attack (TIA).
- Treatment of deep vein thrombosis (DVT) and pulmonary embolism (PE), and prevention of recurrent DVT and PE in adults.

The approval is based on the following pivotal studies:

The **ENGAGE AF-TIMI 48** study (N=21105; mean CHADS₂ score = 2.8) compared edoxaban 60 mg once daily (high-dose regimen) and edoxaban 30 mg once daily (low dose regimen) with dose-adjusted warfarin (International Normalised Ratio [INR] 2.0–3.0) and found that both edoxaban regimens were non-inferior to warfarin in the prevention of stroke and systemic embolism in patients with NVAF. Both edoxaban regimens also provided significant reductions in the risk of haemorrhagic stroke, cardiovascular mortality, major bleeding and intracranial bleeding.²

The **Hokusai-VTE** study (N=8292) in patients with symptomatic VTE had a flexible treatment duration of 3–12 months and found that following initial heparin, edoxaban 60 mg once daily was non-inferior to dose-adjusted warfarin (INR 2.0–3.0) for the prevention of recurrent VTE, and also had a significantly lower risk for the composite of major or non-major clinically relevant bleedings (primary safety outcome).³

Those clinical development programs have been undertaken to support marketing authorisation submissions for edoxaban in those indications. However, as is the case with any medicinal product, real-life use of edoxaban may differ from or extend beyond the patient population that has been studied in the phase 3 program or is included under the approved indication. One of the concerns in real-world use of medicinal practices is the off-label use. Daiichi Sankyo (DS) addressed this concern in the Risk Management Plan (RMP) in order to anticipate necessary risk minimization activities. The potential off-label use of edoxaban in unapproved indications was considered low, because of the availability of approved, indicated and well-established treatment alternatives. However, as it is the case with all other new anticoagulants a residual risk for off-label use might be considered in conditions (for which edoxaban is not approved) that usually also require mid- or long-term anticoagulant treatment or in cases of poor compliance or contraindications of the patient.

Standard routine risk minimisation activities include the communication of the information in the Summary of Product Characteristics (SmPC). In order to further optimise the correct use of the medicinal product by the physician, Daiichi Sankyo Europe GmbH (DSE) is implementing additional risk minimisation activities, namely, prescriber guide as part of the educational programs to make prescribers fully aware of

the approved indications and eligible patients for edoxaban, the dosing recommendations and management of safety concerns. In addition, Patient Alert Cards will be distributed.

The patient alert card is included in every edoxaban package in the European Union (EU).

Furthermore, the DUS, described in this document aims to gain insight on how this new European medicinal product is going to be used in real practice in order to identify prescription patterns, the effectiveness of the educational programs and promptly detect any safety concern, so that pharmacovigilance planning and risk management for edoxaban could be effectively refined, if necessary, on an ongoing basis.

8. RESEARCH QUESTION AND OBJECTIVES

8.1. Primary Objectives

The aim of this DUS is to provide real-world data related to the current prescription patterns of edoxaban. Study objectives are as follows:

To characterize sites and physicians:

- Geographic location of physician site
- Profession or area of primary practice (e.g., GPs, cardiologists, and other specialists
- Patient volume (i.e., number of patients and estimated number of patients using edoxaban).

To characterize users of edoxaban according to:

- Demographic factors (e.g. age, gender, other)
- Patient comorbidity
- Patient subgroups for which there is missing information according to the RMP:
 - o Pregnant and/or breastfeeding women
 - o Paediatric patients
 - Patients with hepatic impairment with coagulopathy and clinically relevant bleeding risk
 - Patients with severe renal impairment (defined as having Creatinine Clearance [CrCl] < 30 ml/min) or end stage renal disease (CrCl < 15 ml/min or on dialysis)
 - o Patients with mechanical heart valves
- Patients being treated with dual antiplatelet therapy

To evaluate the pattern of use of edoxaban:

- Dose (including starting dose) and duration of treatment, including identification of long-term and chronic use, and changes
- Use of concurrent/concomitant medications with special focus on medications
 potentially interacting with edoxaban or contraindicated especially those
 known to increase the risk of bleeding e.g., aspirin, Nonsteroidal AntiInflammatory Drugs (NSAIDs)
- Detect the improbable event of use outside the labelled instructions, including use outside the indication¹ (particularly indications for which alternative anticoagulants are indicated) and use in contraindicated situations.
- History of past use of other anticoagulants

To evaluate the effectiveness of the edoxaban Educational Material as a tool for risk minimization. The specific objectives are:

- To evaluate whether the Educational Material reached the target population (physicians prescribing edoxaban) as part of physician packet provided prior to drug supply
- To assess clinical knowledge: awareness of the target population and the level of knowledge achieved by the educational intervention

9. RESEARCH METHODS

9.1. Study Design

Multinational, multicentre study involving the retrospective chart review of edoxaban users' medical records. Nested in the study, a cross-sectional survey of all participating prescribing physicians will be performed starting from the date of the first data abstraction and repeated over the course of the study to evaluate the effectiveness of the physician educational program.

Being retrospective, this study involves no intervention, and will not impact the usual medical care or affect the treatment of patients. Thus, the study will reflect real-world medical practice without the potential for prescriber response bias which may occur in prospective studies. The inception cohort is defined as patients initiating edoxaban during a 12 month period following the launch of the product in each country.

The study design will allow the evaluation of the effectiveness of the risk minimisation activities targeting the minimisation of any potential off-label use as follows:

On the one hand, the surveys will assess physician' knowledge of the educational materials. But a survey methodology might not be the most appropriate approach for the evaluation of behavior, since surveys collect and analyse self-reported data from healthcare professionals and patients.

Therefore, real-world prescribers' behavior will be assessed by the collection of data from the patients' medical records.

9.2. Setting

The study aims to include approximately 1,200 medical records of consecutive patients who were treated at least once with one or more dose(s) of edoxaban.

9.2.1. Participating Sites

About 100 hospital- and office-based physicians (General Practitioners [GPs], internal medicine physicians and other specialists) in at least 7 Western European countries (Germany, Italy, Switzerland, the United Kingdom, Belgium, Spain and Portugal) are foreseen to participate in the study.

Country selection will take into account prescription volumes, the number of prescribers per capita, and favorable regulatory and ethical environment to conduct observational studies as well as the launch sequence of edoxaban in the different European countries. The sponsor may include additional European country(ies) based upon the actual use of edoxaban in initially-selected countries and to ensure selection reflects geographic representation among European countries.

Following the identification of the countries, an independent prescription data source (IMS LifelinkTM) will be used to identify a representative sample of the prescribers in each country. Based on these sources it is possible to retrieve general information on edoxaban number of prescribers per specialty and geographic region.

At least 100 prescribers of edoxaban will be recruited in 7 European countries following each country-specific product launch and the distribution of the health care professional (HCP) Educational Material. These could include GPs, cardiologists, internal medicine specialists (and other specialists) from a variety of settings (e.g., office-based vs. hospital-based, urban vs. rural).

Physicians participating in interventional programs for edoxaban will not be eligible to participate in the study. By applying this approach both representativeness and comprehensiveness of the sample in terms of types of prescribers are ensured.

In the selected countries, available national prescription databases will be screened to identify geographic and edoxaban prescriber characteristics. Data from IMS LifeLinkTM database for dispensing data in the community care setting, or another appropriate data source, will identify prescribers of edoxaban. This data source will be complementary to the full study and will be obtained prospectively on a quarterly basis, during the study period. On a national level for the targeted countries, the distribution of regional location of the sites as well as the distribution of the prescribers' specialty will be provided. Therefore, IMS LifeLinkTM will be used to refine the a priori sampling strategy for the full study (using regional and specialty distribution of prescribers), and a posteriori to assess the representativeness of prescribers and patients included in the full study. This approach will contribute significantly to the enrolment of a more balanced population of edoxaban and alternative drugs prescribers at both the country and study level to cover broad indications. Potential sites for this DUS must meet the following criteria:

- Willing to provide a list of patients receiving edoxaban
- To allow/have access to patients' source data that are treated with edoxaban
- To be able to complete the study in the EDC system (only in exceptional cases paper CRFs are possible if no access to internet is provided)
- To be able to conduct the study adequately with respect to staff and time capacities.

9.2.2. Source Population

The current study aims to draw conclusions on the pattern of use of edoxaban. Therefore it aims to generalise its conclusions to all users that have been prescribed edoxaban since its launch in Europe.

Sites will be required to maintain a patient enrolment log of eligible patients at their treatment sites. This log will document how patients came to be included or excluded from the study, in order to assess the representativeness of the study population. The overall number of patients and sites may be adjusted during the study to meet enrolment goals, if needed. To the extent possible, consecutive patients meeting inclusion/exclusion criteria will be enrolled.

9.2.2.1. Inclusion criteria

Patients can be enrolled when they had at least one edoxaban prescription record in his/her medical record irrespective of the underlying health condition and with a written informed consent form.

9.2.2.2. Exclusion criteria

No exclusion criteria are defined.

9.2.3. Patient Groups

Not applicable

edoxaban (L1)

9.2.4. Schedule

The inception cohort is defined as patients initiating edoxaban during a 12-month period following the launch of the product in each country.

The eCRF will be used to collect study data. Data collection will be initiated following a study-defined index date, approximately 12 months after product launch (see study milestones; section 6). All study prescribers within a country will be assigned the same index date and will not be contacted prior to the index date. Initiation of prescriber-specific activities for selection of patient records meeting study selection criteria will commence on or following the index date. Data on drug utilisation will be censored on the index date. This approach will ensure that study procedures do not influence prescribing practices.

Figure 1 - Study flow chart per patient

Launch of Edoxaban in other European L1 + M12 L1 + M18 LX + M12 Σ LX + M12 Countries (LX) Inception cohort of first prescibed edoxaban ICF + Data Collection Eligibility period wave = data to be included in DUS Inception cohort of first prescibed edoxaban Eligibility period wave 2 = data to be included in DUS Interim Report Final Report Index date Wave 1 of abstraction Index date Wave X of abstraction First HCP survey Second HCP survey

Notes: DUS: Drug Utilisation Study. HCP: Health Care Professionals. ICF: Informed Consent Form. L1: Launch date in the first European country participating in the study; LX: Launch date in other European countries participating in the study. ΣLX: All medicinal products launched. M12: 12 months later. Final report planned latest 6 months after data base lock.

The launch of edoxaban in other European countries (LX) may also occur before the end of data collection for the first country.

9.2.5. Permanent discontinuation of Study Drug

Not applicable

9.2.6. Withdrawal of Consent from Registry Participation

Not applicable as data will be retrospectively retrieved from patients source data.

9.3. Variables

The following information will be entered in the CRF

I. Site/ Physicians' characteristics

To evaluate the diversity of sites the following information will be collected for each participating site from the site feasibility questionnaire:

- Geographic location of physician site;
- Profession or area of primary practice (e.g., GPs, cardiologists, and other specialists;
- Patient volume (i.e., number of patients and estimated number of patients using edoxaban).

II. Edoxaban treated patient data

1. Demographics and medical history:

- Birth (year/month) or age
- Race/ethnicity (where permitted)
- Height
- Body weight
- Smoking status
- Alcohol consumption
- Diagnosis
- Risk factors and treatment (pharmacological or non-pharmacological) history pertaining to edoxaban treatment
- Cardiovascular comorbidities (including valvular disease) and other relevant somatic comorbidities
- History of haemodialysis

- Relevant familial medical history
- History of past use of other anticoagulants
- Pregnancy and lactation status at the time of prescription
- Time and type of any surgery (including orthopaedic surgery) during the treatment with edoxaban
- Presence of mechanical heart valves
- Pertinent lab tests upon availability including liver function test, CrCl and/or Glomerular Filtration Rate (GFR) pertaining to possible hepatic or renal impairment.

2. Drug utilisation:

- Edoxaban prescription
 - start and end date/ongoing treatment (including repeated prescriptions if any)
 - o daily dose (30 mg, 60mg, other) at the beginning of the treatment and afterwards
 - o reason for use
 - o reason of discontinuation (if applicable)
- Concomitant medications (including if patient is using dual antiplatelet therapy)

III. HCP Educational Material knowledge assessments

1. Survey administration variables:

- o Number of physicians in sample, in total and by key characteristic;
- o Number of physicians attempted to contact
- o Number of physicians effectively contacted
- Number of contacted physicians who agreed to participate
- o Of those agreed to participate, number who completed survey.

2. Description of survey participants

- Medical specialty
- Country
- Setting (type, geography)
- o Experience with edoxaban (yes/no and if yes number of months)
- o Receipt of educational material (yes/no) and time elapsed since its return.

3. Assessment of knowledge of the key messages of the educational program:

- o Frequency and distribution of response to each survey question
- Percentage of respondents indicating correct and incorrect responses to each question
- The success/failure rate of the survey (proportion of correct and incorrect answers) overall and by each section (group of related items)
- Assessment of HCPs' opinion/satisfaction on the utility of educational material.

9.4. Data Sources

DUS

This study is a retrospective chart review. The participating site staff will review the medical charts of the specified number of patients that have been prescribed edoxaban, over the given time period and extract the desired data elements. The data will be entered pseudonymised into electronic Case Report Forms (eCRFs) by the prescribers via a secure web-based electronic data capture (EDC) system. In sites that do not have the capabilities to access the internet to enter data, a provision will be made to collect pseudonymised data recorded on paper CRFs and entered into the study database by the the Sponsor or designee (e.g., Contract Research Organization, CRO) on behalf of the site staff. Data quality will be enhanced through a range of data quality checks that automatically detect out-of-range or anomalous data. These checks will be programmed within the EDC system and system queries will be automatically raised and followed-up by the sponsor/CRO. The data will also be reviewed on an ongoing basis by the sponsor/CRO and manual queries raised as necessary. Further details on validity checks can be found in section 9.6 (Data Management).

Some limitations with regard to data completeness may occur in this study, mainly related to the type and completeness of the information captured in the patients' medical records. Measures to ensure the completion of the eCRF in a systematic, professional, and unbiased manner include:

- eCRF completion guidelines will provide consistent instructions on completion of the eCRF.
- All individuals performing data abstraction from medical records will be trained on appropriate data abstraction techniques in order to minimize possible discrepancies between interpretation of the information recorded by the prescriber in the medical records and the individual performing the review and abstraction of the data.
- Missing data will be followed up during remote monitoring contacts.

To assess the representativeness of the sampled patient population, a screening log of all patients prescribed with edoxaban will be maintained by the site staff, including patient's

age and gender, and whether the patient's chart data was included in the DUS or not. For patient charts that were not captured in the DUS, the reasons for non-inclusion will be documented on the screening log.

Educational Material Evaluation Survey

The survey will be administered either by phone or on line through a secure unique web link concomitantly at the time of the site initiation visit, thus minimizing the impact of any previous reading of the Educational Material by the physician. Six months later, the same Survey will be administered de novo.

The afore-described strategy, together with a comparative analysis of respondents and non-respondents' characteristics, is expected to minimize and detect any response bias or trend among the survey population.

The Educational Material will be distributed to all physicians prior to edoxaban availability and irrespectively from the participation in the DUS. However, investigators participating in the DUS may take part in the survey to assess the physicians' level of awareness and understanding of the content of the educational material/SmPC, including:

- Indications
- o Dosing recommendations and dose reduction
- Populations at higher risk of bleeding
- o Information on switching patients to or from edoxaban
- o Perioperative management
- Temporary discontinuation
- Overdose
- Bleeding complications
- Coagulation testing

Physicians will not be individually assessed. Results will be reported in aggregate form only and not linked to any personal identifier. All information collected during the course of the survey will be kept strictly confidential.

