- o History of past use of other anticoagulants
- Pregnancy and lactation status at the time of prescription
- Time and type of any surgery (including orthopaedic surgery) during the treatment with edoxaban
- Presence of mechanical heart valves
- Pertinent lab tests upon availability including liver function test, CrCl test and/or Glomerular Filtration Rate (GFR) pertaining to possible hepatic or renal impairment.

• Drug utilisation:

- o Edoxaban prescription:
 - start and end date/ongoing treatment (including repeated prescriptions if any)
 - daily dose (30 mg, 60mg, other) at the beginning of the treatment and afterwards
 - reason for use
 - reason of discontinuation (if applicable)
- Concomitant medications (including if patient is using dual antiplatelet therapy).

Health Care Professional (HCP) Educational Material knowledge assessments

- Survey administration variables
- Description of survey participants
- Assessment of knowledge of the key messages of the educational program.

Data Sources

DUS

This study is a retrospective chart review. The identified local site staff will review the medical charts of all patients that have been prescribed edoxaban, over the given time period and extract the desired data elements. The data will be entered pseudonymised into electronic Case Report Forms (eCRFs) via a secure web-based EDC system. In sites that do not have the capabilities to access the internet to enter data, a provision will be made to collect pseudonymised data recorded on paper CRFs and entered into the study database by the Sponsor or designee (e.g. Contract Research Organization, (CRO)) on behalf of the site staff.

To assess the representativeness of the sampled patient population, a screening log of all patients prescribed with edoxaban will be maintained by the site staff, including patient's age and gender, and whether the patient's chart data was included in the DUS or not. For patient charts that

were not captured in the DUS, the reasons for non-inclusion will be documented on the screening log.

Educational Material Evaluation Survey

At the prescribers' primary contact (index date), the physicians will be requested to express their preferences for a means of direct-to-physician contact (email or telephone) in order to complete the survey.

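### The protocol gives two conflicting rules for which charts a site abstracts (all, or an unstated number), and its consecutive fill has no start point, direction or ordering

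*Protocol*

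**What the plan says.** The Summary, under Data Sources, says: "The identified local site staff will review the medical charts of all patients that have been prescribed edoxaban, over the given time period". The parallel sentence in section 9.4 says: "The participating site staff will review the medical charts of the specified number of patients that have been prescribed edoxaban". The protocol gives totals, numbers per country and a number of physicians, but no number, minimum or cap per site.

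The fill rule is consecutive enrolment. Section 9.2 aims for "approximately 1,200 medical records of consecutive patients who were treated at least once with one or more dose(s) of edoxaban". Section 9.2.2 says: "To the extent possible, consecutive patients meeting inclusion/exclusion criteria will be enrolled". Neither gives a starting date, a direction or an ordering variable.

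On timing, section 9.2.4 says: "The inception cohort is defined as patients initiating edoxaban during a 12-month period following the launch of the product in each country". It adds: "Initiation of prescriber-specific activities for selection of patient records meeting study selection criteria will commence on or following the index date". The same section censors drug-utilisation data on the index date.

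Three safeguards are described:
- Section 9.4 requires a screening log of all edoxaban patients, holding age, gender, whether the chart was included and, if not, why.
- Section 9.2.1 uses a prescription database to sample prescribers by region and specialty and to check representativeness afterwards.
- Section 9.9 acknowledges that the need for consent may interfere with consecutive enrolment.

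**The concern.** A site cannot follow both instructions unless its eligible, consenting users happen to equal its number. If it abstracts fewer than all, the consecutive rule decides who enters, and in a retrospective review that rule has no natural origin. In a prospective study, consecutive means from site opening onward. Here the whole 12-month window is already in the records when selection begins.

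Use is censored at a common index date, so a patient's start date fixes the longest time on treatment that can be observed. Section 8.1 makes duration and dose changes objectives. Section 9.7 plans the distribution of time on edoxaban, discontinuations, and prescriptions counted up to the index date. If sites fill from different ends of the window, these summaries mix patients with very different observable time, for reasons unrelated to prescribing. Filling by attendance adds a further problem, because it favours patients still in care and so bears directly on discontinuation.

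**Working it through.** **The plan's own figure.** Section 9.5 gives a half-width of 1.2 points for 5% off-label use with 1,200 charts. The check is 1.96 × √(0.05 × 0.95 / 1,200) = 0.0123, which agrees. All 24 half-widths in Table 6 reproduce in the same way. The sample-size arithmetic is sound. The formula treats charts as a simple random sample, which the selection text does not secure.

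**Inputs from the protocol.** The start window is 12 months per country, selection is on or after the index date, and use is censored at the index date (all 9.2.4). The total is about 1,200 charts (9.2, 9.5), or 600 to 1,200 in the Summary, from about or at least 100 physicians (9.2.1). The average is 1,200 / 100 = 12 charts per physician, or 600 / 100 = 6 at the lower total. These are averages, not caps.

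**Assumptions not in the protocol.** The index date falls exactly at month 12, a site abstracts a fraction f of its starters, and starts follow one of two patterns.

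*Uniform starts.* The earliest fraction f has mean start 6f, so mean observable time is 12 − 6f months. The latest fraction f has mean observable time 6f. A random draw gives 6.

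*Linearly rising starts* (density 2t/144 on 0 to 12). The earliest fraction has mean start 8√f, so observable time is 12 − 8√f. The latest fraction has mean start 8[1 − (1 − f)^1.5]/f, and observable time is 12 minus that. A random draw gives 12 − 8 = 4.

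Mean observable months:

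| f | Uniform, earliest | Uniform, latest | Rising, earliest | Rising, latest |
|---|---|---|---|---|
| 1 | 6.0 | 6.0 | 4.0 | 4.0 |
| 1/2 | 9.0 | 3.0 | 6.3 | 1.7 |
| 1/3 | 10.0 | 2.0 | 7.4 | 1.1 |
| 1/4 | 10.5 | 1.5 | 8.0 | 0.8 |

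At f = 1 the direction is irrelevant. At every smaller fraction the two compliant directions diverge, and neither matches the random draw.

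**Can the log reveal this?** It is named to hold age, gender, inclusion status and reasons, but not start date. The eCRF records start dates (9.3), but only for included patients. A cluster of late starts among included patients therefore cannot be told apart from late uptake at that site.

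**The case against.** The strongest reply is that sites are not left free. Consecutive enrolment is required as far as possible, every edoxaban patient is logged with a reason if not included, and the prescription database serves as a later check. This stands in part. A reader might infer that selection is left to site convenience, but these requirements say otherwise. They still do not fix an origin or direction, and the database outputs named are region and specialty, not timing within a site.

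A reader might also infer that any site with more than 12 users must choose. That does not follow: 12 is an average, section 9.2.2 allows patient and site numbers to be adjusted, and the Summary's milestones are concerned with having enough treated patients. If every site takes all consenting starters, the order does not matter.

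The two instructions may also be closer than they look. The Summary itself provides for charts that are not captured, and a per-site number may sit in a site contract or operations document that is not shown. The Summary nevertheless tells sites to extract data from all, and non-capture could simply mean no consent. The two sentences need reconciling either way.

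Finally, the months tabulated are observable time, not bias in a result, and an analysis that respects censoring could absorb part of the difference. That is fair. Such an analysis cannot supply later months if only late starters were taken, and it cannot undo selection by attendance. Starting dose and reason for use do not depend on length of follow-up.

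**Conclusion.** The point holds as an unresolved conflict between two data-collection instructions, together with a fill rule that has no anchor. It is not a matter for the SAP, which cannot recover charts never abstracted.

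The consequence is conditional: it arises where a site has more consenting starters than it abstracts. There, compliant fills can differ by several months in mean observable time. The gap is 6 months (9 against 3) at half the starters under uniform starts, and about 4.7 months (6.3 against 1.7, before rounding) under rising starts. Duration, dose-change and discontinuation results can be biased as a result. The sampling fraction and the shape of uptake are assumptions.

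A reader might go further and infer that the off-label percentage is distorted by more than the stated precision, or that the study yields no defined estimate of use. The documents do not support that. It would need off-label use to change over the launch window or to differ between high- and low-volume sites, and the protocol neither gives nor excludes either. The safeguards limit the problem but do not close it, because timing is missing from the log.

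**What to change.** Put one rule in the Summary (Data Sources) and in sections 9.2, 9.2.2 and 9.4. Each site lists all patients who started edoxaban in its country's 12-month window. The site criteria in 9.2.1 already ask for something close to this: "Willing to provide a list of patients receiving edoxaban". The site takes all of them or, if there are more than a stated per-site number, approaches them in a random order supplied by the CRO until that number is reached. At the least, fix one start point and direction for all sites.

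Add edoxaban start date and list size to the screening log, so that included and non-included patients can be compared on timing. Table 5 has Wave I recruiting from Q3 2016, so for those sites the log addition may be the only part that can still be applied. Whether to weight charts by list size can be left to the SAP.

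The cost is protocol and site-manual wording, two log fields and a randomised list per site. Filling may be somewhat slower, because sites approach patients in listed order. Written consent will still keep the sample from being fully random.
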